2.8.4.5 Additional Analyses

Time to first occurrence of any AESI with CTC grade > 2 event

Time to first occurrence of an event is defined as time from start of study treatment to the date of first occurrence of this event (or first event within an AESI grouping), i.e. time in days is calculated as (start date of first occurrence of event) – (start of study treatment) +1.

In the absence of an event during the on-treatment period, the censoring date applied will be the earliest of the following dates:

- end date of on-treatment period (end of study treatment + 30 days).
- death date

- start date of new antineoplastic therapy before experiencing any CTC grade ≥ 2 event.
- data cut-off date.
- withdrawal of informed consent date

The corresponding censoring reason will be used: death, new anti cancer therapy, treatment discontinuation, ongoing at cut-off date or consent withdrawal.

Failure curves (ascending Kaplan-Meier curves) will be constructed by cohort. Median together with 95% confidence interval as well as 25th percentile and 75th percentile will be presented for each cohort.

In addition, the median time to occurrence for the subset of patients who experienced the event of interest will be calculated. Simple descriptive statistics, median, min and max as well as 25th percentile and 75th percentile, will be presented.

The same analysis might be repeated for events of grade 3 and grade 4.

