6.1.5 Treatment duration

Patients will be treated until disease progression (radiologically documented according to RECIST v1.1) or until discontinuation of study treatment due to any other reason. In the Core Phase, patients will receive treatment until disease progression, unacceptable toxicity, death, until 18 months after LPFT or discontinuation from the study treatment for any other reason and in the Extension Phase, patients will receive study treatment until discontinuation per Section 7.1.5 until 36 months.

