2.8.1.1 Adverse events of special interest / grouping of AEs

Data analysis of AESIs

An adverse event of special interest is a grouping of adverse events that are of scientific and medical concern specific to compound BYL719. These groupings are defined using MedDRA terms, SMQs (standardized MedDRA queries), HGLTs (high level group terms), HLT (high level terms) and PTs (preferred terms). Customized SMQs (Novartis MedDRA queries, NMQ) may also be used. A NMQ is a customized group of search terms which defines a medical concept for which there is no official SMQ available or the available SMQ does not completely fit the need. It may include a combination of single terms and/or an existing SMQ, narrow or broad. For each specified AESI, number and percentage of patients with at least one event of the AESI occurring during on treatment period will be summarized.

A Case Retrieval Sheet (CRS; an Excel file) with the exact composition of the adverse events groupings is to be used to map reported adverse events to the AESIs groupings (termed Specific Event Categories (SECs) in the CRS). This file may be updated (i.e. it is a living document) based on review of accumulating trial data. The latest version of the CRS document available at the time of the analyses will be used.

Summaries of these AESIs will be provided by cohort (specifying grade, SAE, relationship, leading to treatment discontinuation, leading to dose adjustment/interruption, hospitalization, death etc.). If sufficient number of events occurred, analysis of time to first occurrence will be applied.

Depending on the observed number of events, the time to first occurrence of any CTC grade > 2 AESI may be summarized using Kaplan-Meier methods for specific groupings.

Median time to onset and 95% CI will be summarized. Ascending Kaplan-Meier lots will be generated.

A listing of all grouping levels down to the MedDRA preferred terms used to define each AESI will be generated.

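### Time to first grade >2 AESI: the planned 1 minus Kaplan-Meier curve censors death and treatment stop, so it exceeds the share of patients affected, by little for early toxicities and by more only if onset is later (minor)

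*SAP*

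**What the plan says.** SAP Amendment 4, section 2.8.4.5, defines time from start of study treatment to the first AESI of grade >2. A patient without an event in the on-treatment period is censored at the earliest of five dates: "end date of on-treatment period (end of study treatment + 30 days"), death, start of new antineoplastic therapy, data cut-off, or withdrawal of consent. The reason is kept: "The corresponding censoring reason will be used: death, new anti cancer therapy, treatment discontinuation, ongoing at cut-off date or consent withdrawal". The display is then fixed: "Failure curves (ascending Kaplan-Meier curves) will be constructed by cohort", and "Median together with 95% confidence interval as well as 25th percentile and 75th percentile will be presented for each cohort". Simple onset-time descriptives among patients who had the event are also planned.

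Section 2.8.1.1 covers the same analysis in softer terms: "Depending on the observed number of events, the time to first occurrence of any CTC grade > 2 AESI may be summarized using Kaplan-Meier methods". It adds "Median time to onset and 95% CI will be summarized". It also reports the crude result for every AESI: "number and percentage of patients with at least one event of the AESI occurring during on treatment period will be summarized".

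Neither section plans a cumulative incidence or competing-risks estimate. Neither says that the curve describes risk in a setting where nobody dies or stops treatment.

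**The concern.** The event is a first AESI within the on-treatment period. Once a patient has died, or the period has ended, that event can no longer occur. Kaplan-Meier treats such patients as if they remained exposed to the same future risk as those still on treatment. One minus Kaplan-Meier is therefore at least as large as the proportion of patients affected, and it is larger whenever event-free patients leave before others have the event.

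Most exits here are of that kind. Protocol section 6.1.5 says "Patients will be treated until disease progression (radiologically documented according to RECIST v1.1") or until another reason for stopping, and the sample-size section assumes a median PFS below 6 months after CDK4/6 failure. The Amendment 6 summary reports 9 of 380 patients still on treatment (2.4%), so administrative censoring plays a small part late in the study.

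Safety by cohort is a secondary objective, and a reader will naturally take an ascending curve as the percentage of patients affected by month t.

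**Working it through.** The SAP states no figure for these curves, so there is nothing to reproduce. The check compares the planned quantity with the proportion affected.

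**Inputs**
- Exit rate d from the risk set (stop, death or new therapy), taken as constant. Base case: 45% remaining at 6 months (the planning alternative), d = -ln(0.45)/6 = 0.1331 per month. Favourable bound: median 11.0 months (the SOLAR-1 PFS in Protocol 1.2.4.2), d = ln 2/11 = 0.0630. Also medians of 6 and 4 months, and 30% remaining at 6 months (the null in the Protocol summary), d = 0.2007. Using progression-free figures for time on treatment is an assumption.
- Tail L = 1 month after stopping, standing for the 30 days. Death or new therapy within that month shortens the tail, so results without it are also given where they differ.
- AESI rate h. The documents give no onset distribution, so all patterns are assumed. Hyperglycemia is placed in month 1 (Protocol 6.3.2.1.3) and skin toxicity within 2 months (Protocol 6.3.2.1.2).

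**Formulas**
- Planned curve: 1-KM(t) = 1 - exp(-H(t)), where H is the cumulative AESI hazard.
- Proportion affected: CIF(t) = integral from 0 to t of h(u) exp(-H(u)) G(u) du, with G(u) = 1 up to L and exp(-d(u-L)) afterwards.
- For constant h: CIF(t) = (1 - e^(-hL)) + e^(-hL) × h/(h+d) × (1 - e^(-(h+d)(t-L))).

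**Base case, h = 2% per month, 18 months**
- 1-KM = 1 - exp(-0.36) = 30.2%.
- CIF = 0.0198 + 0.9802 × (0.02/0.1531) × (1 - exp(-0.1531 × 17)) = 0.0198 + 0.1186 = 13.8%.
- Ratio 2.18. A simulation at n = 112 gave 30.7% against 13.9%.

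**Ratio of 1-KM to CIF at 18 months, with the tail**

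| Time on treatment | Onset within 2 months (1-KM 40%) | Constant 2%/month (1-KM 30.2%) | 2%/month from month 6 only (1-KM 21.3%) |
|---|---|---|---|
| Median 11 months | 1.01 | 1.52 | 1.92 |
| Median 6 months | 1.02 | 2.02 | 3.21 |
| 45% at 6 months | 1.03 | 2.18 | 3.78 |
| Median 4 months | 1.04 | 2.57 | 5.44 |
| 30% at 6 months | 1.04 | 2.84 | 6.91 |

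If all onset falls in month 1 (1-KM 60%), the ratio is 1.00 throughout. Without any tail, onset within 2 months gives 1.06 to 1.19 over the same exit rates.

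**A rate from the protocol.** SOLAR-1 reports grade ≥3 diarrhea in 7% (Protocol 1.2.4.2). Assume a constant hazard and no tail.
- Matching 7% to this trial's base exit rate: h = 0.07 × 0.1331/0.93 = 0.0100. At 18 months, 1-KM is 16.5% and CIF 6.5%, a gap of 10.0 points.
- The 7% arose with an 11-month median PFS, so the hazard is better scaled to that exposure: h = 0.07 × 0.0630/0.93 = 0.0047. Then 1-KM is 8.2% and CIF 3.2%, a gap of 5.0 points. The ratio stays above 2.

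**Quartiles and medians.** With constant h, 1-KM reaches 25% at -ln(0.75)/h and 50% at ln 2/h.
- At 2%/month it reaches 25% at 14.4 months, while the base-case CIF can never exceed 0.0198 + 0.9802 × 0.1306 = 14.8%.
- At 5%/month it reaches 50% at 13.9 months, while CIF at 24 months is 30.5%.
- At the 7% diarrhea rate 1-KM is still below 25% at 18 months.

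**The case against.** The strongest defence is that censoring at treatment stop targets risk while on treatment. That is a legitimate quantity, whereas cumulative incidence falls simply because patients stop early. Stopping does not abolish toxicity either: Protocol 8.2.2 still requires related serious events to be reported after 30 days. This stands in part, as the choice is partly one of estimand. But the SAP does not state that estimand, and it does not cover death. It also needs exits to be independent of AESI risk, which is doubtful when patients stop for progression or for other toxicity.

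The proportion affected is already reported. Crude counts and percentages appear for every AESI, and onset times are described among those affected. No test or decision rule depends on the curve. All of this stands and keeps the point minor.

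Section 2.8.1.1 makes the Kaplan-Meier summary depend on the number of events, so rare AESIs may never be plotted. At n = 112, 7% is about 8 patients. This also stands, although section 2.8.4.5 says without condition that curves will be drawn.

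The only onset times in the documents are early, and the AESI list itself sits in the Investigator Brochure and a case retrieval file. A reader might infer that late toxicities will look two or three times as frequent as they are. That needs an onset pattern the documents do not supply. The osteonecrosis rate of 4.2% (Protocol, use of bone modifying agents) does not supply it: no grade is given, and it is not identified as an AESI.

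**Conclusion.** The point holds as a minor one. The planned curve censors death, end of treatment + 30 days and new therapy, carries no label as a hypothetical on-treatment risk, and exceeds the proportion of patients with the event.

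- For the early toxicities the protocol describes, the excess is about 0 to 4% in relative terms with the 30-day tail, and somewhat more where death or new therapy cuts the tail short.
- At 18 months it is about 1.5 to 2.5-fold if the AESI rate is constant (2.8-fold at the null proportion of 0.30), and larger if onset is late. These figures rest on assumed onset patterns and on progression-free figures standing in for time on treatment.

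A reader might also infer that medians or quartiles will appear reached when fewer patients than that had the event. The rates in the documents do not show this. It arises only if the AESI rate is about 2% per month or more for a quartile, and higher (5% per month in the example) for a median.

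Crude AESI counts and percentages, the primary test and the sample size are unaffected.

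**What to change.** In SAP sections 2.8.4.5 and 2.8.1.1, wherever the time-to-AESI analysis is done:

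- Display the Aalen-Johansen cumulative incidence by cohort. Treat death, end of the on-treatment period (+30 days) and new antineoplastic therapy as competing events, and censor only at data cut-off and consent withdrawal.
- Report it at fixed times, for example 1, 3, 6 and 12 months, with 95% confidence intervals.
- Keep the onset-time descriptives among affected patients.
- If 1 minus Kaplan-Meier is retained, label it as hypothetical risk while on treatment and show it beside the cumulative incidence.

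The same edit should settle whether the curves are conditional (2.8.1.1) or always produced (2.8.4.5). It should also align the grade: the analysis is of grade >2 events, but the new-therapy censoring rule refers to grade ≥2.

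The cost is SAP wording and standard programming. The exit reasons are already recorded and need only be split into competing events and true censoring. The drawback is that a median time to onset will be estimable less often.

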2.8.5 Safety data for Extension Phase

Safety analyses for the Extension Phase will be performed on the Safety Set in Extension Phase. The assessment of safety will be based mainly on the duration of exposure and dosage. The following summaries will be provided since the start of Core Phase:

- Duration of exposure to study treatment;
- Dose of study treatment received;
- Dose adjustments and discontinuation of study treatment.

2.9 Pharmacokinetic endpoints

Not applicable.

2.10 PD and PK/PD analyses

Not applicable.

2.11 Patient-reported outcomes

Not applicable.

2.12 CCI

CCI

CCI

Table 2-8 CCI

CCI

CCI

Table 2-9

CCI

CCI

CCI

CCI

2.13 Other Exploratory analyses

Not applicable.

2.14 Interim analysis

The first Interim Analysis (IA) is planned after at least **CCI** patients receiving alpelisib plus fulvestrant (cohort A) have at least 6 months of follow up. Once **CCI** patients will be recruited, the interim analysis data cutoff will be the last patients first visit plus 6 months. The second IA is planned after **CCI** patients have been treated (regardless of cohort) and have at least 6 months of follow-up on study. The third IA will be performed after the Core Phase has ended.

At the time of the first two IAs, preliminary efficacy (ORR, CBR) as well as key safety data will be analyzed in a descriptive fashion. The primary endpoint will not be analyzed and no statistical hypothesis will be tested.

The third IA will include all efficacy and safety data up to the end of the Core Phase.

Primary endpoint will not be analysed and no formal statistical hypothesis testing will be done at the time of IA and therefore no multiplicity adjustment will be made.

Preliminary efficacy as well as key safety data will be analysed in a descriptive fashion separately in each cohort.

The following endpoints will be summarized at the time of the first two IAs:

- Overall response rate (ORR)
- Clinical Benefit rate (CBR)
- Average daily dose, cumulative dose, relative dose intensity
- Duration of exposure
- Dose reduction/interuptions
- Adverse events
- Serious adverse events
- Deaths
- Adverse event of special interest (AESI)
- Laboratory parameters

3 Sample size calculation

3.1 Primary analysis

A median PFS of at least 6 months (or 50% of patients who are alive without progression after 6 months) has been observed for alpelisib 300 mg plus fulvestrant 500 mg and also for palbociclib 125 mg plus fulvestrant 500 mg in PiK3CA mutant patients previously treated with AI (without CDK4/6 inhibitor) in [CBYL719X2101] and Paloma-3 ([Cristofanilli 2016](#)) studies respectively. Currently, there is no available clinical data in post-CDK4/6 inhibitor setting in PIK3CA mutant patients. Assuming that these patients after failure to CDK4/6 inhibitor will have a lower median PFS than 6 months, a proportion of **CCI** of patients alive without progression after 6 months is considered as a clinically meaningful threshold in both cohorts for this study and was used for sample size calculation.

The sample size is based on an exact Binomial test for single proportion to test the null hypothesis $H_0: p \leq CCI$ where p is the proportion of patients who are alive without progression at 6 months. With a one-sided 2.5% level of significance (two-sided 95% CI), a total sample size of 112 patients in each cohort is required in order to have a power of at least 90% when the true $p \geq 0.45$. [Table 3-1](#) provides the operating characteristics for $N=112$ and different true rates.

Table 3-1 Operating Characteristics

Sample size (N)	True rate	Prob (X≥44 True rate)
112	CCI	

The study will enroll a total of approximately 340 patients who have PIK3CA mutation with at least 112 patients allocated into each Cohort A (alpelisib + fulvestrant), Cohort B (alpelisib + letrozole) and Cohort C (alpelisib + fulvestrant).

At the time of the first two Interim Analysis (IA) preliminary efficacy (ORR, CBR) will be analyzed in a descriptive fashion. The primary endpoint will not be analyzed and no statistical hypothesis will be tested. Therefore no multiplicity adjustment was made.

4 Change to protocol specified analyses

4.1 Impact of COVID-19

Due to pandemic COVID in year 2020, some extra analyses will be performed outside protocol specified.

Operational impact: Specified protocol deviation categories will be assigned to important deviations related to COVID-19 (e.g., missing efficacy assessments) and these will be summarized and listed separately. A summary table of the COVID-19 related deviations by relationship category will be provided.

Safety: To help to evaluate the impact of the pandemic on safety, the incidence of COVID-19 related adverse event preferred terms will be presented incorporating COVID-19 related adverse events with an onset date in the year of 2020.

Efficacy: If there are $\geq 10\%$ patients with missed visits due to COVID-19, an additional sensitivity analysis for primary endpoint will be performed to address the potential impact of the COVID-19 pandemic, using local investigator assessment using RECIST v1.1 on the mFAS and considering the visit labeled by “missed visits due to COVID-19” has the same assessment value as in previous scheduled visit.

5 Appendix 1

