Any potentially measurable lesion that has been previously treated with radiotherapy should be considered as a non-measurable lesion. However, if a lesion previously treated with radiotherapy has clearly progressed since the radiotherapy, it can be considered as a measurable lesion.

Each lesion that is measured at baseline must be measured by the same method (either same radiologic/nuclear method or by physical exam) throughout the study so that the comparison is consistent. Criteria required for determining partial or complete response should be present for at least 4 weeks.

Chest x-rays and ultrasound should not be used to measure tumor lesions.

Core Phase Treatment phase imaging assessments

Imaging assessments as described in Table 7-3 should be performed using the same imaging modality used at screening, irrespective of study treatment interruption or actual dosing. Imaging assessments for response evaluation will be performed every 12 weeks (+/- 7 days) during the Core Phase. The 12 week interval should be followed regardless of whether study treatment is temporarily withheld or unscheduled assessments are performed.

Additional imaging assessments may be performed at any time during the study at the investigator's discretion to support the efficacy evaluations for a subject, as necessary. Clinical suspicion of disease progression at any time requires a physical examination and imaging assessments to be performed promptly rather than waiting for the next scheduled imaging assessment.

Each lesion that is measured at screening must be measured by the same method (either same imaging method or by photography, including a metric ruler) and when possible, the same local radiologist/physician throughout the study so that the comparison is consistent. If an off-schedule imaging assessment is performed because progression is suspected, subsequent imaging assessments should be performed in accordance with the original imaging schedule.

Combined Positron Emission Tomography/Computed Tomography (PET/CT) may be used only if the CT is of similar diagnostic quality as a CT performed without PET, including the utilization of IV contrast media. At the discretion of the Investigators, FDG-PET scans may be performed to document progressive disease per RECIST v1.1 (Appendix 5).

Extension Phase

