- 3. If the patient discontinues fulvestrant on or after Cycle 2 Day 1, then:
 - the last date of exposure to fulvestrant is calculated as (last date of administration of fulvestrant) + (length of time interval - 1) i.e. [last date of fulvestrant administration+ (28-1)].
 - If the patient died or was lost to follow-up within last date of administration of fulvestrant + 27 days, the last date of exposure to fulvestrant is the date of death or the date of last contact, respectively.

Goserelin and Leuprolide

Goserelin and leuprolide were administered (for pre menopausal women and men (cohort B)) on the first day of every cycle (e.g. Cycle 1 Day 1, Cycle 2 Day 1 etc.)

The *last date of exposure to* Goserelina or leuprolide is calculated as follows:

- (last date of administration of Goserelina or leuprolide) + (length of time interval - 1) i.e. [last date of Goserelina or leuprolide administration+ (28-1)].
- If the patient died or was lost to follow-up within last date of administration of Goserelina or leuprolide + 27 days, the last date of exposure to Goserelina or leuprolide is the date of death or the date of last contact, respectively.

Study day

The study day, describes the day of the event or assessment date, relative to the reference start date.

The study day is defined as:

- The date of the event (visit date, onset date of an event, assessment date etc.) – reference start date + 1 if event is on or after the reference start date;
- The date of the event (visit date, onset date of an event, assessment date etc.) – reference start date if event precedes the reference start date.

The reference date for all assessments (safety, efficacy, etc) is the start of any component of the study treatment.

Time unit

A year length is defined as 365.25 days. A month length is 30.4375 days (365.25/12). If duration is reported in months, duration in days will be divided by 30.4375. If duration is reported in years, duration in days will be divided by 365.25.

Baseline

For safety and efficacy evaluations, the last available assessment on or before the date of start of study treatment is defined as “baseline” assessment.

If patients have no value as defined above, the baseline result will be missing.

On-treatment assessment/event and observation periods

For adverse event reporting the overall observation period will be divided into three mutually exclusive segments:

- ***pre-treatment period:***

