2.3.2 Patient disposition in Extension Phase

Patient disposition in Extension Phase will be summarized using the Safety Set in Extension Phase. The following summaries will be provided:

- Number (%) of patients who are still on-treatment in Extension Phase (based on the 'End of Extension Treatment Phase' page not completed);
- Number (%) of patients who discontinued the Extension study treatment phase (based on the 'End of Extension Treatment Phase' page)
- Primary reason for Extension study treatment phase discontinuation (based on the 'End of Extension Treatment Phase' page)

Protocol deviations

The number (%) of patients in the FAS with any protocol deviation will be tabulated by deviation category (as specified in the study Data Handling Plan) and by cohort. Protocol deviations leading to exclusion from analysis sets will be tabulated separately by cohort. All protocol deviations will be listed.

Additional protocol deviation summaries will be provided to address the potential impact of COVID-19 pandemic in each cohort. The number and percentage of patients in the FAS with any protocol deviation with one of the following relationships will be summarized by deviation category: COVID-19 health status related, COVID-19 situation: Site issue, COVID-19 situation: Lockdown / Quarantine of patient, COVID-19 situation: Patient concern, COVID-19 situation: Drug supply issue and COVID-19 situation: Other.

Analysis sets

The number (%) of patients in each analysis set (defined in [Section 2.3](#)) will be summarized by cohort.

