2.7.1 Secondary endpoints

The mFAS will be used for the secondary efficacy analyses.

Progression free survival

Secondary endpoints include PFS, defined as the time from the date of start of treatment to the date of the first documented progression or death due to any cause. PFS will be based on local investigators review of tumor assessments and using RECIST 1.1 criteria (see Appendix 5 of the study protocol). If a patient has not progressed or died at the analysis cut-off date, PFS will be censored at the date of the last adequate tumor evaluation date before the cut-off date. PFS events documented after the initiation of new anti-neoplastic therapy (i.e. RECIST 1.1 documented disease progression or death) will be considered for the primary analysis provided tumor assessments continue after initiation of new cancer therapy. Discontinuation due to disease progression (collected on the 'End of treatment' and 'End of post treatment follow up' disposition pages) without supporting objective evidence satisfying progression criteria per RECIST 1.1 will not be considered disease progression for PFS derivation. Clinical deterioration will not be considered as a qualifying event for progression.

Overall response rate

ORR is defined as the proportion of patients with best overall response (BOR) of complete response (CR) or partial response (PR) according to RECIST 1.1 (see Appendix 5 of the study protocol). ORR will be calculated based using local investigators review of tumor assessment data in patients with measurable disease at baseline. Patients with only non-measurable disease at baseline will be part of the analysis and will be included in the numerator only if a complete response was observed. Tumor assessments performed before the start of any further antineoplastic therapy (i.e. any additional secondary antineoplastic therapy or surgery) will be considered in the assessment of BOR.

Clinical benefit rate (CBR)

CBR is defined as the proportion of patients with a best overall response of CR or PR, or an overall lesion response of stable disease (SD) lasting 24 weeks or longer or Non-CR/ Non-PD lasting 24 weeks or longer, according to RECIST 1.1 criteria. A patient will be considered to have SD for 24 weeks or longer if a SD response is recorded at 23 weeks or later from

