enrollment, allowing for the +1 week visit window for tumor assessments. Patients with only non-measurable disease at baseline will be part of the analysis and will be included in the numerator only if they achieve a complete response or have a 'Non-CR/Non-PD' response 23 weeks or more after start of study treatment. CBR will be calculated using the mFAS based on the investigators' tumor assessments.

Duration of response

Duration of response (DOR) only applies to patients whose best overall response is complete response (CR) or partial response (PR) according to RECIST 1.1 based on local investigators review of tumor assessment data. The start date is the date of first documented response of CR or PR (i.e., the start date of response, not the date when response was confirmed), and the end date is defined as the date of the first documented progression or death due to underlying cancer. Patients continuing without progression or death due to underlying cancer will be censored at the date of their last adequate tumor assessment using the censoring rule described for PFS analysis (options A(1), C2(1), D(1), E(1), F(1-3) and G(1) from Table 3-2 in Appendix 5 of the study protocol).

Overall Survival

OS is defined as the time from date of start treatment to date of death due to any cause. If a patient is not known to have died, then OS will be censored at the date of last known date patient alive.

PFS after next-line of treatment (PFS2)

PFS2 is defined as time from date of start of treatment to the first documented disease progression (clinical or radiologic) on next-line therapy or death from any cause, whichever occurs first. The first documented progression on next-line treatment will be based on investigator assessment of PD (i.e. as captured on the anti-neoplastic therapy after treatment discontinuation CRF page).

1. Next-line therapy is defined as the first new (systemic) anti-neoplastic therapy initiated after discontinuation of study treatment regardless of EoT reason. Drugs given as part of the same regimen should be grouped as one line (i.e. part of the next-line therapy). In addition, continuation of the study treatment after the initial radiologic disease progression will not be considered as next-line therapy.
2. PFS2 will be censored if no PFS2 event (progression or death) is observed during next-line therapy before the analysis cut-off date; the censoring date will be the last contact date.

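### Clinical benefit rate times stable disease from enrollment instead of start of treatment, and the only COVID-19 sensitivity analysis of the primary endpoint can raise the result but not lower it

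*SAP*

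**What the plan says.** **Clinical benefit rate (SAP 2.7.1).** Stable disease qualifies as lasting 24 weeks "if a SD response is recorded at 23 weeks or later from", and the sentence continues "enrollment, allowing for the +1 week visit window for tumor assessments". For patients with only non-measurable disease, the same paragraph requires a Non-CR/Non-PD "response 23 weeks or more after start of study treatment". SAP 2.1.1 sets the general rule: "The reference date for all assessments (safety, efficacy, etc) is the start of any component of the study treatment". The protocol glossary defines enrollment as entry into the study, at the point where consent must be obtained.

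**COVID-19 analysis (SAP 4.1).** If at least 10% of patients have visits missed because of COVID-19, the primary endpoint is re-analysed on the mFAS. A visit labelled as missed for that reason "has the same assessment value as in previous scheduled visit". No other COVID-19 analysis of the primary endpoint is planned. The protocol schedule (7.2.1.1) is: "Imaging assessments for response evaluation will be performed every 12 weeks (+/- 7 days) during the Core Phase". The primary endpoint uses scans in weeks 23 to 25 (SAP 2.5.3). On reporting, SAP 2.3.2 says: "Additional protocol deviation summaries will be provided to address the potential impact of COVID-19 pandemic in each cohort". SAP 4.1 gives missing efficacy assessments as an example of the deviations to be summarised and listed.

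**The concern.** The two clinical-benefit clocks disagree within one paragraph. Consent comes before the first dose, so the stable-disease clock starts earlier. Disease control shorter than 23 weeks on treatment can then count as benefit, but only in patients with measurable disease.

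A sensitivity analysis for missed scans should show how far the result could shift in either direction. This one fills the gap with a value that is almost always favourable: a patient with progression at week 12 is already a failure, so what is carried forward to week 24 is non-progression. If the report shows only this analysis beside the primary result, agreement between the two says little about robustness.

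**Working it through.** **Clinical benefit clock.** 23 weeks is 161 days. Take main consent at day -21 to day -1 (Protocol 7.1.2 and Table 7-1). Then 161 days from consent is 161 - 21 = 140 days (20.0 weeks) to 161 - 1 = 160 days (22.9 weeks) after first dose. Scheduled scans fall at weeks 11 to 13 and 23 to 25. A week-13 scan is at most 16 weeks from consent and fails both clocks; a week-23 scan passes both. Only unscheduled scans, or the end-of-treatment scan required when the last one is older than 30 days (Protocol 7.1.5), can fall in the gap. Each such patient adds 1/112 = 0.9 percentage points.

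**The plan's own rule.** With N=112, H0 p ≤ 0.30 (protocol summary, data analysis) and success at 44 or more, the exact binomial gives a type I error of 0.0225 and power of 0.9055 at p=0.45. The Clopper-Pearson lower limit is 29.4% for 43/112 and 30.2% for 44/112. The cut-off of 44 reproduces.

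**Direction of the COVID-19 analysis.** Let k be documented successes and m the missed week-24 scans with non-progression at week 12. Carry-forward gives (k+m)/112. The primary estimate depends on how a missing scan is scored:

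- as failure: k/112, which is lower whenever m > 0;
- excluded: k/(112-m), which is never higher, because (k+m)(112-m) - 112k = m(112-m-k) ≥ 0;
- not a failure: (k+m)/112, unchanged.

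Carry-forward is therefore never below the primary estimate. A week-12 value that is itself missing or unknown is not covered by the text.

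**Size, illustrative.** Assume a constant hazard (week-12 non-progression = √p), 10% of week-24 scans missed independently of outcome (0.10 × 112 = 11.2), and a share d of week 12–24 events still recorded as failures through death, discontinuation or off-schedule imaging. The last is realistic, because "Clinical suspicion of disease progression at any time requires a physical examination and imaging assessments to be performed promptly". Then:

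- true successes among the missed = 11.2p;
- false successes under carry-forward = 11.2(1-d)(√p - p).

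At p=0.30, √p = 0.548 and true successes are 3.36:

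| d | Carry-forward successes | Of which false | Gap to missed = failure |
|---|---|---|---|
| 0 | 6.13 | 2.77 | 5.5 points |
| 0.5 | 4.75 | 1.39 | 4.2 points |
| 0.75 | 4.05 | 0.69 | 3.6 points |

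Scoring every missed scan as failure loses the 3.36 true successes. At p=0.45 the false successes are 2.47, 1.24 and 0.62, against 5.04 lost. With 5% or 20% missed, all counts halve or double.

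**How far apart the two scorings can be.** An extreme case: 32 documented successes and 12 missed scans, all non-progressing at week 12. Missed = failure gives 32/112 = 28.6%, and the rule is not met. Carry-forward gives 44/112 = 39.3% with lower limit 30.2%, and the rule is met.

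**The case against.** The strongest reply is that the primary analysis may already be the worst case. SAP 2.5.3 lists progression, death and study discontinuation as failures and does not mention a patient on study without a week 23–25 scan. The mFAS denominator is fixed, however, and non-success is the natural reading. On that reading, a rejection of H0 in the primary analysis cannot be undone by any treatment of missed scans, and carry-forward rightly shows the favourable side. This stands, and it is why the remedy is to present the two results together. The unstated scoring rule is a clarification only: SAP 5.1 refers imputation rules to a PDS that is not among the documents.

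Carry-forward is also nearer the truth than missed = failure in every scenario computed above. That stands too.

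A reader might infer that carry-forward inflates the trial's type I error. At p=0.30, with 10% missed and d=0, it would reach 44 with probability 0.077, against 0.0225 with complete data. The documents do not support that inference: this is a conditional supportive analysis, no decision rests on it, and the primary result does not change. Nor do they support saying that missed scans go unreported. COVID-19 deviations are to be summarised and listed by cohort; what is not specified is a count of missed week-24 scans. The 10% trigger counts missed visits of any kind, so the share of week-24 scans lost may be well below 10%.

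On clinical benefit, the general reference-date rule in SAP 2.1.1 shows what was probably intended. The specific sentence still says otherwise, and a programmer could follow it.

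**Conclusion.** The clinical-benefit rule is wrong as written and contradicts both its own paragraph and SAP 2.1.1. Its effect is probably small, since it touches only off-schedule stable-disease scans at about weeks 20.0 to 22.9, on an endpoint without a formal test. That range assumes enrollment means main consent on day -21 to -1.

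The COVID-19 analysis is legitimate as a favourable bound but insufficient alone, because it can raise the primary estimate or leave it unchanged and cannot lower it. The one-sidedness follows from the 12-week schedule and holds under each reading of the missing-scan rule, apart from an unknown or missing week-12 value. The sizes are illustrative, resting on a constant hazard, an assumed share of missed scans and outcome-independent missingness. They show errors in opposite directions (overcount 0.7 to 2.8, undercount 3.4 at p=0.30), so neither scoring should be presented as unbiased. This is a modest improvement to reporting and no challenge to the primary result.

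**What to change.** **SAP 2.7.1:** replace *from enrollment* by *from start of study treatment*. This is a one-phrase correction; the clinical benefit rate could fall slightly.

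**SAP 4.1:** keep the carry-forward analysis and label it the favourable bound. Show beside it, per cohort, the result with every missed week-24 scan scored as failure. If that is already the primary analysis, say so and present the two together. Report per cohort how many week-24 scans were missed because of COVID-19.

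The cost is a few sentences and minor programming, with no new data. The COVID-19 picture may look less favourable. Enrolment was complete by 14-Dec-2020, so six months' follow-up puts the last primary cut-off at about mid-June 2021, before the SAP amendment of 24-Mar-2022. The added display is therefore supportive and should leave completed primary results as they are.
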